## PROTOCOL SUMMARY

Title:	Targeting Auditory Hallucinations with Alternating Current Stimulation
Précis:	
The purpose to determine the efficacy of transcranial alternating current stimulation, tACS, versus sham stimulation (with tDCS versus sham as a positive control for assay sensitivity) for the treatment of medication-refractory auditory hallucinations in patients with schizophrenia. We will recruit 48 males and females diagnosed with schizophrenia or schizo-affective disorder. Eligible participants will have 5, twice-daily (one week Monday through Friday), 20 minute stimulation sessions. Stimulation will be at least 3 hours apart. Participants will be randomly assigned to one of three groups; sham stimulation, 10 Hz (alpha) tACS or 2 mA tDCS. Participation will involve 1 to 8 visits. At the initial session, informed consent will be obtained and subjects will be screened for eligibility. Eligible participants will then be scheduled for their, twice-daily stimulation sessions which will include daily assessment of stimulation side-effects. Clinical assessments will be performed at baseline, 1, 2 and 4 weeks using the Auditory Hallucinations Rating Scale (Attachment 3). Neurophysiological (EEG) and cognitive assays will be performed before and after stimulation. Please see Appendix A for a detailed schematic describing all visits and assessments.

Objectives:	
Our primary objective is to demonstrate the value of synchronization and information flow measures derived from EEG data as novel biomarkers in the treatment of medication refractory auditory hallucinations in schizophrenia with transcranial current stimulation. To reach this objective, we will test the working hypothesis that (1) baseline impairment in EEG synchronization and information flow predicts treatment success and (2) changes in these markers correlate with improvement of clinical symptom presentation as determined by the AHRS, PANSS, and BACS (Attachment 12). We will test our working hypothesis by measuring whole-head EEG data from all patients in our feasibility study (48 patients from Aim 1) before and

immediately after the five day course of stimulation and at both follow-up visits.

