### **3.2 Study Outcome Measures**

#### **3.2.1 Primary Outcome Measures**

The Auditory Hallucination Rating Scale (*Attachment 3*) will be the primary outcome measure for this study. This rating will be administered at baseline, two weeks later at the screening visit, the first day of stimulation, last day of stimulation, at the one week and the one month follow up visits. We will compare the AHRS scores immediately before the first stimulation session and immediately after the last stimulation session as our primary outcome measure.

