# 11 STATISTICAL CONSIDERATIONS

## 11.1 Study Hypotheses

### 11.1.1 Primary Objective

*Null hypothesis:* There is no difference in AHRS score immediately before first stimulation session and immediately after last stimulation session between treatment groups.

*Alternative hypothesis:* There is a difference in AHRS score immediately before first stimulation session and immediately after last stimulation session between treatment groups.

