### 11.1.2 Secondary Objectives

1. *Null hypothesis:* There is no difference in changes of alpha frequency power between baseline EEG and EEG at completion of stimulation between treatment groups.

*Alternative hypothesis:* There is a difference in changes of alpha frequency power between baseline EEG and EEG at completion of stimulation between treatment groups.

2. *Null hypothesis:* There is no difference in PANSS score immediately before first stimulation session and immediately after last stimulation session between treatment groups.

*Alternative hypothesis:* There is a difference in PANSS score immediately before first stimulation session and immediately after last stimulation session between treatment groups.

3. *Null hypothesis:* There is no difference in BACS score immediately before first stimulation session and immediately after last stimulation session between treatment groups.

*Alternative hypothesis:* There is a difference in BACS score immediately before first stimulation session and immediately after last stimulation session between treatment groups.

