## 11.3 Final Analysis Plan

We will perform spectral analysis of resting state EEG before and after stimulation treatment and use a mixed ANOVA with the within subject factor session (immediately before first stimulation session and immediately after last stimulation session) and between subject factor treatment (sham, 10Hz tACS or 2 mA tDCS). Spectral analysis will be performed with multi-tapered estimation of the frequency spectrum followed by integration over the classical alpha EEG band (8-12 Hz). We will apply the same statistical analysis procedure for our primary outcome of AHRS, PANSS and BACS scores.

We will also use post-hoc paired or unpaired Student's t-test to identify the group or groups that differed. We will further control for multiple comparisons by using Bonferroni corrections.

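### Section 11.3 lets paired t-tests decide which arms differed, but a within-arm test cannot show a difference from sham; ANCOVA on the Day 1 score is a low-cost second improvement

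*Combined protocol and SAP*

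**What the plan says.** The primary null hypothesis (section 11.1.1) is "There is no difference in AHRS score immediately before first stimulation session and immediately after last stimulation session between treatment groups". The secondary hypotheses in section 11.1.2 have the same between-group form for PANSS, BACS and alpha power. The Protocol Summary gives the purpose as efficacy of tACS against sham, "with tDCS versus sham as a positive control for assay sensitivity".

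Section 11.3 specifies a mixed ANOVA with session (before the first and after the last stimulation) as the within-subject factor and treatment as the between-subject factor. It is set out for alpha power and then extended: "We will apply the same statistical analysis procedure for our primary outcome of AHRS, PANSS and BACS scores". The follow-up step reads "We will also use post-hoc paired or unpaired" Student's t-tests "to identify the group or groups that differed", and then "We will further control for multiple comparisons by using Bonferroni corrections".

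The plan does not say:
- which of the two t-tests answers which question;
- whether a significant interaction is required first;
- whether the unpaired test uses change scores or Day 5 scores;
- how many comparisons are in the Bonferroni family.

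No baseline-adjusted analysis is planned.

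**The concern.** The only purpose given for the post-hoc tests is to find the arms that differed, and a paired test is allowed for it. Arms given frequent attention and an active sham may all improve. A paired test on the tACS arm then detects that common improvement, whether or not tACS adds anything to sham.

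The two obvious safeguards do not help:
- Bonferroni lowers the significance level but leaves the hypothesis tested unchanged.
- A significant-ANOVA gate protects only when no arm differs. This trial includes an arm meant to work, so tDCS can open the gate for tACS.

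Section 11.2 describes a pilot as the basis for deciding whether a treatment goes on to a large controlled trial. A tACS effect that is really improvement shared with sham would mislead that decision.

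A separate and lesser point concerns precision. With two sessions, the session-by-treatment term is the same test as a one-way ANOVA on change scores. It is valid under randomization, but it fixes the slope on the Day 1 score at 1. ANCOVA estimates that slope. Precision matters at 16 per arm, where section 11.2 claims power only for a large effect.

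**Working it through.** **Inputs.** From the documents: three arms of 16 (section 11.2); Day 1 and Day 5 scores as the primary comparison (section 3.2.1: "We will compare the AHRS scores immediately before the first stimulation session and immediately after the last stimulation session as our primary outcome measure"); Bonferroni correction (section 11.3). The plan states no power, alpha or effect size as a number, so there is no figure of its own to reproduce.

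Assumed, because the documents do not give them: two-sided overall alpha of 0.05; family size k = 3, 6 or 9; normally distributed change with SD 1; improvement c shared by all arms, 0 to 0.7 SD; extra tDCS benefit e, 0.8 to 1.2 SD; Day 1 to Day 5 correlation rho, 0.3 to 0.9; SD ratio s = SD Day 5 / SD Day 1, 0.8 to 1.25.

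**Step 1. Paired test alone, no gate.** The paired t has noncentrality c × √16 = 4c on 15 df. At alpha 0.05/3 the critical value is 2.694. For c = 0.25, 0.5 and 0.7 the noncentrality is 1.0, 2.0 and 2.8, so the test is significant with probability 6.9%, 28.0% and 55.5% in an arm identical to sham.

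**Step 2. Can tDCS alone open the gate?** With mean changes (c, c, c+e) for sham, tACS and tDCS, the ANOVA noncentrality is 16 × (2/3)e² on 2 and 45 df. For e = 0.8, 1.0 and 1.2 it is 6.83, 10.67 and 15.36. Power at 0.05 is 61%, 81% and 93%, so it usually can.

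**Step 3. Only tDCS works and the ANOVA is positive** (200,000 simulated trials per scenario, k = 3). Ranges are over e:

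| Shared improvement c | tACS paired test significant | tACS significant, sham not | Unpaired tACS-sham significant |
|---|---|---|---|
| 0.25 | 6% | 5-6% | 0.9-1.4% |
| 0.5 | 23-27% | 19-20% | 0.9-1.4% |
| 0.7 | 48-54% | 25-27% | 0.9-1.4% |

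At c = 0 and 0.1 the tACS paired rate is under 1% and about 2%. A larger family shrinks the rates but leaves the gap. For c = 0.25, 0.5 and 0.7 the paired rates are 3.5%, 16-18% and 37-42% at k = 6 (unpaired 0.4-0.7%), and 2.5-2.7%, 13-14% and 31-36% at k = 9 (unpaired 0.3-0.5%).

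As a share of all trials the numbers are smaller. At c = 0.5 and e = 0.8, 23% of the 61% with a positive ANOVA is 0.23 × 0.61 = 14%.

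**Step 4. All arms equal.** An active arm is paired-significant while sham is not in 2-3% of trials if gated. Without the gate it is 12%, 35% and 36% at c = 0.25, 0.5 and 0.7 (k = 3).

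**Step 5. ANCOVA against change scores.** The large-sample variance ratio is s²(1 − rho²)/(1 + s² − 2·s·rho). For example, s = 1 and rho = 0.7 gives 0.51/0.60 = 0.85; s = 1.25 and rho = 0.8 gives 0.5625/0.5625 = 1.00. The ratio never exceeds 1, before a cost of about 2% for estimating the slope at N = 48 (44/43 = 1.023). Power below is for a tACS-sham difference of 0.8 SD of change at alpha 0.05/3; change scores give 42% throughout.

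| s | Variance ratio at rho 0.3, 0.5, 0.7, 0.8, 0.9 | ANCOVA power, same order |
|---|---|---|
| 0.8 | 0.50, 0.57, 0.63, 0.64, 0.61 | 75, 68, 63, 62, 65% |
| 1 | 0.65, 0.75, 0.85, 0.90, 0.95 | 62, 54, 49, 46, 43% |
| 1.25 | 0.78, 0.89, 0.98, 1.00, 0.95 | 52, 46, 42, 41, 43% |

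**The case against.** The main test is sound: the interaction term tests exactly the between-group hypotheses, and the post-hoc sentence also offers the unpaired test. With one within-subject and one between-subject factor, paired may have been meant for session and unpaired for treatment. Nothing says a paired result alone would be reported as superiority to sham. That limits the flaw to the follow-up step. It does not remove it, because the purpose clause covers both tests and no other section restricts the paired one.

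The size is conditional. It needs an effective tDCS arm, an ineffective tACS arm, shared improvement, a positive ANOVA, and an analyst who relies on the paired result. The screening rule of at most 20% AHRS change (section 4) may limit drift, though it does not exclude sham response. The 48-54% figure also includes many trials in which sham is paired-significant too, where a tACS-specific claim is less likely. The tACS-but-not-sham column is the fairer measure of misleading results. As a share of all trials with e = 0.8 it is 3%, 12% and 17% at c = 0.25, 0.5 and 0.7. All of this stands, and it bears on how often harm would occur, not on whether the test answers the question.

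ANCOVA is a refinement, not the repair of an error. Its gain is about 1 point of power at s = 1 and rho = 0.9, and the stability rule makes a high correlation plausible. The largest gains need the Day 5 SD to shrink, which nothing in the documents supports. That also stands.

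**Conclusion.** The concern holds. As written, section 11.3 allows a test without sham data to support a statement about which arms differ, and neither Bonferroni nor an ANOVA gate protects tACS when tDCS works. That logical flaw depends on no numerical assumption.

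Its size does: the false tACS signal runs from negligible with no shared improvement to about a quarter of ANOVA-positive trials (tACS significant, sham not) at 0.7 SD, against roughly 1% with the between-arm test. These figures rest on normal changes, equal variances, k = 3, and a tDCS benefit of 0.8 to 1.2 SD with none for tACS.

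The ANCOVA part holds as a secondary improvement. It ranges from a substantial gain to a loss of about 1 point of power over the grid examined. It should be adopted for its low cost, not because the planned interaction test is wrong.

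**What to change.** 1. In section 11.3, remove the paired test from the step that identifies differing arms, for AHRS, PANSS, BACS and alpha power. Suggested text: *Arms that differ will be identified only by between-arm contrasts; within-arm change is reported descriptively.* This change stands even if the mixed ANOVA is kept; the unpaired tests should then be stated to use change scores.

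2. For AHRS, PANSS and BACS, analyse the Day 5 score by ANCOVA with treatment as factor and the Day 1 score as covariate. Take all arm comparisons, including tACS versus sham and tDCS versus sham, from that model.

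3. State the number of contrasts in the Bonferroni family.

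Alpha power is left out of item 2 because its baseline is described inconsistently: at screening in sections 3.2.2 and 7.2 and Appendix A, but on Day 1 of stimulation in sections 8.2.2 and 14.3. That must be settled before an EEG covariate can be named.

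The cost is a change of wording. Section 7.3 already collects the Day 1 scores for the three scales, and no visit, participant or measurement is added. ANCOVA uses one degree of freedom (44 instead of 45).

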## 12 SOURCE DOCUMENTS AND ACCESS TO SOURCE DATA/DOCUMENTS

### **Human Research Committee (IRB):**

- All IRB Correspondences are on file.
- The study staff is IRB approved prior to performing any study procedures.
- Adverse events and deviations are reported to IRB per current guidelines.
- All versions of the IRB protocols and informed consent forms are on file.

### **Informed Consent:**

- Ensure that participant identification is on all pages of the ICF
- There is documentation that the participant is given a copy of the consent form (*Appendix G*)
- The participant and study representative signed and dated the consent form for him/herself.
- The participant initialed and dated all appropriate pages on the informed consent form.
- Note to file (*Appendix N*) made for any informed consent deviations.
- Ensure a valid (current version date) copy of the consent form was used.

### **Protocol:**

- Confirm that the study staff is conducting the study in compliance with the protocol approved by IRB
- The protocol deviations (exceptions and violations) are documented in the participant chart and reported to IRB as required.

### **Source Documents:**

- Each participant binder will contain a checklist to ensure that each binder has each source document. The checklist will be dated by the researcher for each time an assessment is administered. (*Appendix J*)
- Review participant charts to ensure the accuracy, completeness and legibility of the data
- Any correction made to the source documents is dated, initialed, and explained. The original entry should not be obscured.
- The protocol specific source documents are on file.
- Source documents are completed in ink.
- Note to files (*Appendix N*) are made for missing or incomplete data and to explain any discrepancies or additional comments.

### **Electronic Case Report Forms (eCRF)**

- Ensure the data reported on the eCRF is consistent with the source documents.
- Discrepancies between the source documents and eCRF are explained in a note to file (*Appendix J*) or captured in a comment in the eCRF.

**DNA**

- Participant names will not be on any of the samples collected at the initial session. DNA testing is performed within the University of North Carolina at Chapel Hill and the samples are not shared with or processed by any third party outside the university.

The research coordinator, research assistants, and PI will have access to all of the above information. Co-I and medical monitor will have access to files upon request as they will need access to the locked rooms and filing cabinets in which these documents are located. The key linking dummy identifiers with subject information will be securely destroyed after completion of data acquisition.

## **13 ETHICS/PROTECTION OF HUMAN PARTICIPANTS**

### **13.1 Ethical Standard**

The investigator will ensure that this study is conducted in full conformity with the principles set forth in The Belmont Report: Ethical Principles and Guidelines for the Protection of Human Subjects of Research, as drafted by the US National Commission for the Protection of Human Subjects of Biomedical and Behavioral Research (April 18, 1979) and codified in 45 CFR Part 46 and/or the ICH E6; 62 Federal Regulations 25691 (1997).

### **13.2 Institutional Review Board**

The Office of Human Research Ethics is responsible for ethical and regulatory oversight of research at UNC-Chapel Hill that involves human participants. The OHRE administers, supports, and guides the work of the Institutional Review Boards and all related activities. Any research involving human participants proposed by faculty, staff, or students must be reviewed and approved by an IRB before research may begin, and before related grants may be funded. OHRE and the IRBs are critical components of the coordinated Human Research Protection Program, which serves to protect the rights and welfare of human participants. All components of this program must work together to ensure institutional compliance with ethical principles and regulatory requirements. The following is a mission statement for the coordinated Human Research Protection Program:

The University of North Carolina at Chapel Hill is committed to expanding and disseminating knowledge for the benefit of the people of North Carolina and the world. An important part of that commitment to knowledge is research of the highest quality on all aspects of the health and behavior of people, and such research is only possible through the participation of humans as research participants. Human participants are partners in research and a precious resource to the university. At UNC-Chapel Hill, human participant research is a privilege, but not a right. Consistent with that philosophy, it is the mission of the UNC-Chapel Hill Human Research Protection Program to ensure that

1. The rights and welfare of human participants are paramount in the research process;
2. The highest standards of ethical conduct are employed in all research involving human participants;
3. Research investigators are properly trained in the ethical and regulatory aspects of research with human participants;

4. Research investigators deal honestly and fairly with human participants, informing them fully of procedures to be followed, and the risks and benefits of participating in research; and
5. Research using human participants at UNC-Chapel Hill conforms to all applicable local, state, and federal laws and regulations and the policies of the university.

### **13.3 Informed Consent Process**

Informed consent is a process that is initiated prior to the individual's agreeing to participate in the study and continues throughout the individual's study participation. Extensive discussion of risks and possible benefits of tACS will be provided to the participants and their families. Consent forms describing, in detail, the study intervention, device, procedures, and risks are given to the participant and written documentation of informed consent is required prior to the administration of any treatment or assessments used in this study. *Please see Appendix G for an example of the Documentation of Informed Consent Process form.* All consent forms will be IRB-approved and updated with any new information as modifications are made throughout the study (*Appendix F*).

Together, the researcher and potential participants will review the clinical trial in its entirety. At several intervals during the consent review, the researcher will ask the participant questions that will assess the comprehension of the information in the consent. If the participant is unsure or does not know, the researcher will return to that section and more carefully explain the information. Participants must sign the informed consent document prior to any procedures taking place. If needed, the participants will have the opportunity to discuss the study with their surrogates or think about it prior to agreeing to participate. Participants may withdraw consent at any time throughout the course of the trial. A copy of the signed informed consent document will be given to the participants for their records. The rights and welfare of the participants will be protected by emphasizing to them that the quality of their medical care will not be adversely affected if they decline to participate in this study.

### **13.4 Exclusion of Women, Minorities, and Children (Special Populations)**

Non-English speaking individuals are excluded because the ability to accurately and completely communicate study information, answer questions about the study, and obtain consent is necessary. Female participants will be asked if there is any reason to believe they might be pregnant. Pregnant participants will be excluded despite the fact that theoretical risk to mother or fetus is exceedingly small, since no safety data for pregnancy is known to exist for transcranial

current stimulation studies. All women of child-bearing potential will be asked to take a pregnancy test during the initial session in order to determine eligibility for the study.

### **13.5 Participant Confidentiality**

Participant confidentiality is strictly held in trust by the participating investigators, their staff, and the research team. This confidentiality is extended to cover testing of biological samples and genetic tests in addition to the clinical information relating to participants.

All data will only be referenced by dummy identifier code. Data will be stored on a password protected computer. A key connecting names and code numbers will be kept in a locked cabinet, accessible only by research personnel. All data will be stored and analyzed on password protected computers, also only accessible by research personnel. Participants will not be identified in any report or publication about this study.

### **13.6 Study Discontinuation**

In the event that the study is discontinued, participants who have completed or who are still enrolled in the study will be notified. Any new information gained during the course of the study that might affect participant's willingness to continue will be communicated within 2 days of the PI learning this information.

## **14 DATA HANDLING AND RECORD KEEPING**

The study coordinator and research assistants are responsible for the accuracy, completeness, legibility, and timeliness of the data reported. During weekly meetings, the data will be reviewed by the PI to check for completeness and continued safety of the participants and research staff. Any changes made to the data will involve crossing out the original data, documenting the new data with the initials and date of the researcher making the change.

